## **5.2. Drug Supplies**

### **5.2.1. Formulation and Packaging**

Study medication will be supplied by Pfizer as capsules of pregabalin (50, 75, 100, 150, 200, 225, and 300 mg), as well as 20 mg/mL solution. The pregabalin liquid oral solution formulation (20 mg/mL) and the pregabalin oral capsules are bioequivalent. The pregabalin capsules are formulated into size #0 gray/gray capsules. All study medication is to be packaged in bottles that are child-resistant.

Pregabalin capsules are composed of pregabalin, lactose monohydrate, cornstarch, and talc encapsulated in opaque hard gelatin capsule shells composed of gelatin and titanium dioxide. Pregabalin oral solution contains a sweetening agent (sucralose) and a flavor (artificial strawberry).

### **5.2.2. Preparation and Dispensing**

The Investigator will receive shipments of clinical drug supplies and must verify and acknowledge the receipt of the clinical drug supplies and retain related documentation.

The Sponsor will provide study medication that will be dispensed through an interactive voice response system (IVRS). The supplies will be identified by the IVRS using a container number. The IVRS will monitor the study medication inventory and re-supply as necessary.

The study medication will be dispensed at Visit 1 through Visit 8. The 1-week taper medication will be dispensed at Visit 8, or for those subjects who discontinue before completing the study, between Visits 3 and 7.

Additional bottles of placebo will be provided to each site for subjects to be able to test their ability to swallow the size #0 capsules. These bottles will be clearly labeled for this purpose.

### **5.2.3. Administration**

Pregabalin will be administered orally daily in 2 equally divided doses (BID; approximately q12 hr) in subjects  $\geq$ 4 years of age or in 3 equally divided doses (TID; approximately q8 hr) in subjects  $<$ 4 years of age, as specified in [Section 5.1- Allocation to Treatment](#). Subjects weighing  $<$ 30 kg will receive pregabalin as a liquid formulation. Pediatric and adult subjects

with body weight  $\geq 30$  kg may choose either liquid or capsule formulation based on subject preference and ability to swallow the size # 0 capsules. Study medication formulation for administration will be as outlined below, with investigators (and subjects) determining the choice of solution or capsule for children and adults  $>30$  kg.

If a subject missed a dose, subject should skip the dose and wait until the next scheduled dose for administration. No additional study medication administration (ie, double-dosing) is allowed at any time during the study.

Weight	Formulation
<30 kg	Liquid
Pediatric subjects $\geq 30$ kg	Liquid or capsule
Adult subjects	Capsules or liquid

#### 5.2.4. Compliance

Subjects will take the study medication according to the instructions provided, and should adhere to the dosing schedule as closely as possible, with study medication administered approximately every 12 hr (ie, q12 hours) in subjects  $\geq 4$  years of age or in 3 equally divided doses (ie, q8 hours) in subjects  $<4$  years of age. Compliance will be defined as the percentage of required doses that were ingested. Subjects who are consistently not compliant with the dosing regimen should be evaluated by the Investigator and discussed with the Pfizer clinician for possible discontinuation from the study.

For subjects who begin taking capsules, but can no longer comply with swallowing after starting, parents/caregivers should break open the capsules and sprinkle the study drug into food for ingestion until the next study visit. Sprinkling should only occur when the child is in danger of missing a dose due to inability to swallow the capsules and there is no liquid dose available at that time. All of the food that the capsule has been sprinkled on must be ingested. This should be noted in the Dosing Diaries and dosing log CRFs. At the next study visit, the site should record the days that the study drug was sprinkled, and then switch the subject to the liquid oral solution form of the study drug for the remainder of the study. An unplanned visit may be scheduled to switch from capsules to liquid if necessary.

If the subject regurgitates or spits out the study drug within 15 minutes after either liquid or capsule administration, the subject/parent/caregiver should re-administer the study drug. If more than 15 minutes have elapsed since drug was taken, no additional study drug should be administered until the next scheduled dose. This occurrence should be noted in the Dosing Diaries and dosing log CRFs.

Administration of the liquid oral solution through a nasogastric (NG) feeding tube will be permitted and should be documented accordingly. If a subject has an NG tube that was inserted prior to entry into the study, it should be documented in the subjects' "Medical History". If a subject has an NG tube inserted during the course of the study, it should be documented in the subjects' "Concomitant Treatments" as a non-drug treatment. Specifying whether the NG tube was inserted or removed during the study is important to document.

### **5.3. Drug Storage and Drug Accountability**

It is the site's responsibility to handle and store the clinical study supplies under secure and locked conditions. Note that pregabalin, is a controlled substance (CV) in the US, and therefore in the US must be stored according to US/Federal Drug Enforcement Agency (DEA) regulations. The US sites will provide a copy of the DEA license, and proper state/local license if applicable, to the Sponsor. For those countries where pregabalin is not a controlled substance, the sites are to comply with their local regulations.

Study medication must be stored at 15-25°C. Access to the stored study medication should be limited to the Investigator, the Study Coordinator, and the Pharmacist (when applicable). The Investigator, or an approved representative, eg, Pharmacist, will ensure that all study medications are stored in a secured area, under recommended storage conditions and in accordance with applicable regulatory requirements. If the study medication is determined to have been stored or delivered outside the outlined temperature range, the information is to be brought to the appropriate study supply personnel for evaluation.

Storage conditions stated in the investigator brochure may be superseded by the label storage.

Study medication will be dispensed under the supervision of investigator site personnel. Each subject will complete a dosing diary and will bring the diary and the medication bottle(s) back to the clinic at each visit. For those subjects who are dispensed capsules, a pill count will be done by the site staff at each visit, and the subject/caregiver will be queried about any missed or extra doses taken. For those subjects who are dispensed liquid oral solution, medication bottles will be weighed by the site staff when dispensed. The bottles will again be weighed when returned at each visit, in order to determine the approximate volume of study medication consumed. The subject/caregiver will be queried about any missed or extra doses taken or any volume discrepancies.

All dispensed study medication bottles will be locally kept available for checks by the study monitor.

The Investigator must maintain adequate records documenting the receipt, use, loss, or other disposition of the investigational product(s). All medication bottles dispensed to study subjects must be returned to the Investigator. A Pfizer-approved drug accountability form must be used. The form must identify the investigational product, including batch or code numbers, and account for its disposition on a subject-by-subject basis, including specific dates and quantities. The forms must be signed by the individual who dispensed the drug, and copies must be provided to Pfizer.

Unused study drug and unused or used study drug materials must be kept in a secure location for final accountability and reconciliation. At the end of the clinical study all drug supplies unallocated or unused will be returned to a Pfizer vendor for destruction by completing the Destruction of Investigational Product Form. The Investigator must provide an explanation for any destroyed or missing study drug and/or study drug materials. Pfizer may authorize destruction at the study site, and the Investigator must ensure that the materials are destroyed

in compliance with applicable environmental regulations, institutional policy, and any special instructions provided by Pfizer. Destruction must be adequately documented.

#### **5.4. Concomitant Medication(s)**

Prior and concomitant medication information will be collected for all subjects for a period of 30 days prior to screening (for subjects enrolling directly into Study A0081106) and during the study. Once enrolled, any medication a subject takes other than the study medication specified by the protocol is considered a concomitant medication. This includes all antiepileptic medications. All concomitant medication must be recorded in the subject's medical record and on the appropriate Case Report Form (CRF) page. Information collected must include medication, reason for use, start date and stop date.

##### **5.4.1. Permitted Medications**

The Investigator must be informed of all medications the subject receives prior to the subject's participation in the study. The following listing of medications/classes of medications is meant to provide guidance regarding permitted medications but should not be considered a comprehensive list. A member of the Pfizer study team may be consulted for assistance in determining whether or not specific medications not contained on this list should be permitted or prohibited. Initiation of new medications, including AEDs, during study participation is allowed if medically indicated. Initiation of certain drugs, however, such as CNS active compounds, like Risperidone, should be discussed with the study clinician. If there are any questions about the start of a new drug, the study clinician should be contacted.

Anti-epileptic drugs (including VNS) are permitted and the number and dosages are at the discretion of the investigator. Changes in the dose, regimen and type of AED are allowed during the study participation upon the discretion of the investigator.

Non-prescription medications, including herbal and home remedies, are also considered concomitant medications and should be recorded, along with other medications on the Concomitant Medication Log of the Case Report Form (CRF).

Examples of medications or classes of medications for which Episodic Use is permitted:

- Acetaminophen/paracetamol.
- Aspirin (chronic use also permitted).
- Bronchodilators (chronic use also permitted).
- Inhaled steroids (chronic use also permitted).
- Non-steroidal anti-inflammatory drugs (NSAIDs).
- Over the counter medications (excluding medications such as Kava Kava or St. John's Wort).

Examples of medications or classes of medications for which Chronic Use is permitted:

- Antihypertensive agents.
- Lipid lowering agents.
- Medications to treat ADHD [ie, stimulants (eg, methylphenidate; amphetamine); selective norepinephrine reuptake inhibitors (eg, atomoxetine); alpha agonists (eg, clonidine; guanifacine)].
- Antiepileptic drugs.
- Aspirin.
- Bronchodilators.
- Inhaled steroids.
- Multivitamins.
- NSAIDs.
- Oral and depot contraceptives.

#### **5.4.2. Prohibited Medications**

Concurrent treatment with other investigational agents or devices is not allowed during the study. **Note:** a previously implanted Vagus Nerve Stimulator (VNS) is allowed but will be considered as a concomitant AED.

The use of felbamate, gabapentin or vigabatrin is prohibited during the study.

Administration of CNS – active compounds, regardless of indication, is prohibited during the study, with the following exceptions:

- Prescribed medications consistent with inclusion/exclusion criteria.
- Use of PRN benzodiazepines (See Section 5.5).

The washout period of all centrally- acting compounds (CNS-active) that have to be discontinued per protocol has to be at least 2 weeks prior to screening Visit 1.

#### **5.5. Benzodiazepine Use as Needed for Occasional Seizure Exacerbation**

Benzodiazepines may be used as needed (PRN) during this open-label study. Use of PRN benzodiazepines will be permitted for the occasional seizure exacerbation. PRN benzodiazepine use should not exceed a total of 6 dosage administrations in any given 3 month period.

If a benzodiazepine is prescribed for treatment on a regular basis (eg, weekly) then it is considered one of the 3 allowed AEDs. In such cases, additional benzodiazepines may also be used PRN as described above.

## 6. STUDY PROCEDURES

The study schedule of events and the specific procedures performed at each visit are shown in the [Schedule of Activities](#). A subject may be seen at any time for reasons of safety.

### 6.1. Clinic Visit 1A (Day 1A): Screening for Subjects who have participated in Studies A0081041, A0081042, or A0081105

The last day of Studies A0081041, A0081042, and A0081105 will be designated Day 1 of this study. The subject may be screened, and if inclusion and exclusion criteria are met, enrolled into Study A0081106 after all procedures have been completed for Studies A0081041, A0081042, or A0081105. For subjects who have participated in, but did not complete Studies A0081041, A0081042, or A0081105, eligibility for Study A0081106 will be reviewed with a member of the Pfizer study team to determine further eligibility. Subjects are required to have completed a minimum of 4 weeks of double-blind treatment in Studies A0081041 or A0081105 to be considered potentially eligible for Study A0081106. The following activities will be performed at Visit 1:

- Obtain written informed consent from both (if available) of the child's legal representatives (parents or guardians) and obtain the child's assent (if applicable). For adult subjects written informed consent will be obtained from the subject, or if necessary, a legally acceptable representative (parent or guardians).
- Review eligibility per inclusion/exclusion criteria.
- Record demographic data (eg, date of birth, sex [at birth], race, etc).
- Record medical history including primary diagnosis.
- Record seizure history including classify seizure type.
- Record ongoing adverse events from Studies A0081041, A0081042, or A0081105 if appropriate.
- Record all ongoing concomitant medications and non-drug treatments/procedures from Studies A0081041, A0081042, or A0081105 if appropriate.
- Evaluate study medication compliance from Studies A0081041, A0081105 and A0081042.
- Assign subject number and dispense study medication via telerandomization system.
- Dispense subject daily seizure and dosing diary.

- The following assessments are not required to be completed at this visit as the results from Studies A0081041, A0081042, or A0081105 will be used: medical history including seizure related history and antiepileptic medication history; all prior medications; blood samples for hematology and chemistry; urine sample for urinalysis; full physical examination to include height, weight and vital signs and assessment of Tanner Stage for pediatric/adolescent subjects less than 16 years of age; full neurological examination; urine pregnancy test for female subjects who are menarchal, if the results of the urine pregnancy test are positive, the subject will not be eligible for study participation; 12-lead electrocardiogram; CogState battery (completed as part of the last visit of Study A0081041 only); assessment of suicidal ideation and behavior (C-SSRS Since Last Visit version or CBCL) using appropriate test for subject's age.

Note: From Visit 1 onwards, weight of subjects will be recorded in the IVRS at every visit during the course of the study in order to adjust the volume and/or dose of study medication dispensed according to weight change to ensure appropriate study medication administration.

## **6.2. Clinic Visit 1B (Day 1B): Screening for Subjects Directly Enrolling into Study A0081106 who have not Participated in Studies A0081041, A0081042, or A0081105**

Prior to study entry the following screening procedures will be performed at Visit 1:

- Obtain written informed consent from both parents (if available), or the child's legally acceptable representatives and obtain the child's assent (if applicable).
- Review eligibility per inclusion/exclusion criteria.
- Review and record adverse events.
- Record demographic data (eg, date of birth, sex [at birth], race, etc).
- Record medical history including primary diagnosis.
- Record seizure history including classify seizure type.
- Verify subjects have had an average of at least 3 seizures per month in the 3 months prior to screening. There must not be any seizure free months in the 3 months prior to screening.
- Record complete medical history including seizure related history and antiepileptic medication history.
- Perform complete full physical exam which includes vital signs, including blood pressure (BP) (sitting), pulse and assessment of Tanner Stage for pediatric/adolescent subjects <16 years of age.

- Record height and weight.

Note: From Visit 1 onwards, weight of subjects will be recorded in the IVRS at every visit during the course of the study in order to adjust the volume and/or dose of study medication dispensed according to weight change to ensure appropriate study medication administration.

- Perform full neurological examination.
- Perform electroencephalogram (EEG) (unless the procedure has been performed within 24 months prior to the Screening Visit).
- Perform contrast-enhanced computed tomography (CT) or magnetic resonance imaging (MRI) scan of the brain if it has not been performed within 60 months prior to the Screening Visit or if it is clinically warranted.

Note: in the event that a CT or MRI scan is needed, it should be performed as soon as possible after Visit 1 if it cannot be performed on the day of this visit and must be completed and reviewed prior to Visit 2.

- Record all concomitant medications and non-drug treatments/procedures currently and within 30 days of Visit 1.
- Perform, review and transmit 12-lead ECG to central reader.
- Administer CogState battery (POS subjects 4-16 years of age).
- Perform urine pregnancy test for female subjects who are menarchal. If the results of the urine pregnancy test are positive, the subject will not be eligible for study participation.
- Collect blood and urine specimens for clinical laboratory assessments. If it is not feasible to obtain a urine sample then no urine sample will be required.

**Note:** In the event that the subject has an exclusionary abnormal screening laboratory value (see [Exclusion Criteria 5](#)) the laboratory test should be repeated. If the repeated test is still abnormal, the subject should be withdrawn from the study at Visit 2. In the event that the subject has an abnormal laboratory value that the investigator determines is significant and exclusionary, the subject should be contacted to stop taking study medication and return to the clinic for an early termination visit.

- Administer the MINI-KID and C-SSRS Lifetime or Child Behavioral Checklist (CBCL) as appropriate for subject's age. If CBCL is administered, scores must be obtained as soon as possible. If positive scores are obtained on the CBCL or CSSRS, a mental health risk assessment must be performed by a qualified mental health professional prior to randomization.

- Assign subject number and dispense study medication via tele-randomization system.
- For direct-enrolling subjects that will receive liquid solution, train parents on dosing administration and demonstrate use of oral syringe/bottles. Have subject and/or child's parents/legally acceptable representative practice dosing in office to verify comprehension of dosing instructions.
- Administer first dose of study medication in office.

Note: all screening procedures must be completed before subject is administered the first dose of study medication. All eligibility criteria should be confirmed prior to, or on Visit 2. If a subject is not deemed eligible, subject should be notified by phone to discontinue study medication, and should come back for an Early Termination visit as soon as possible.

- Dispense subject daily seizure and dosing diary and train subject and/or child's parents/legally acceptable representative on its use and completion.

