Collect Blood and Urine Samples for Clinical Laboratory Assessments	X b	X								X						X	
Suicidality Assessments: Child Behavior Checklist (CBCL)/MINI-KID, C-SSRS “Lifetime” f	X b	X															
Suicidality Assessments Child Behavior Checklist (CBCL)/CSSRS “Since Last Visit”	X b		X	X	X		X		X			X			X	X	
Complete CogState Battery h	X b	X														X	
IVRS assignment	X	X															
Dispense Daily Seizure and Dosing Diary	X	X	X	X	X		X		X			X			X		
Collect and Review Seizure/Dosing Diary			X	X	X		X		X			X			X	X	

Study Period		Screening/ Baseline		12 Month Treatment Phase												End of Treatment & Taper Phase	
Clinic Visit Number		Visit 1A	Visit 1B	Visit 2	Visit 3	Visit 4	TC*	Visit 5	TC*	Visit 6	TC*	Visit 7	TC*	Visit 8	Visit 9		
Study Month		Prior Study Subjects	Direct Enroll	Month 1	Month 2	Month 3	Month 4	Month 5	Month 6	Month 7	Month 8	Month 9	Month 10	Month 11	Month 12/EOS/ Early Term g Begin Taper	End Taper/ Follow up	
Study Day	Day 1A a	Day 1B a		8 (±1)	30 (±4)	60 (±4)	90 (±4)	120 (±4)	150 (±4)	180 (±4)	210 (±4)	240 (±4)	270 (±4)	300 (±4)	330 (±4)	365 (±7)	7 days post completion i (±3)
Dosing Compliance Training/Review and Demonstration		X	X				X		X		X	X		X	X		
Evaluate Study Medication Compliance	X		X	X	X	X	X	X	X	X	X	X	X	X	X	X	
* Telephone contact to assess dosing and diary compliance, concomitant medications and AE's						X		X		X	X		X	X			
Dispense Study Medication	X	X j	X k	X k	X k		X k		X k			X k			X e		
Assess and Record Adverse Events	X	X	X	X	X	X	X	X	X	X	X	X	X	X	X	X	

a. **Visit 1A = Screening Visit for subjects from A0081041, A0081042, or A0081105:** This visit should be completed for subjects who previously participated in double-blind Studies A0081041, A0081042 or A0081105. These subjects will enroll into Study A0081106 on the last day of the double-blind study with no interruption in their pregabalin treatment.

**Visit 1B = Direct-Enroll Screening Visit:** This visit should be completed for subjects who did NOT participate in Studies A0081041, A0081042, or A0081105. These subjects will enroll directly into Study A0081106 to initiate treatment with open label pregabalin and must complete all of the screening assessment noted under Visit 1B.

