- g. Month 12, Visit 8 is the End of Treatment/End of Study visit for subjects who will not initiate taper of pregabalin per the discretion of the investigator. Visit 8 will be the final study visit for these subjects. For subjects who will taper their pregabalin treatment, Visit 8 is considered End of Treatment/End of Study Visit but they will initiate taper at this visit and return for a follow-up Visit 9 to end taper. For early terminations, all Visit 8 procedures should be performed and if taper is initiated, subjects should return for follow-up Visit 9.
- h. Cogstate Battery will be completed only for pediatric partial onset seizure subjects (Protocol A0081041) 4-16 years of age.
- i. The follow-up visit is only required for subjects who received taper medication.
- j. All screening procedures must be completed prior to administration of first study medication. All eligibility criteria should be confirmed prior to, or on, Visit 2.
- k. Adjust the dose if needed based on seizure response and tolerability.

\* TC = Telephone Contact to assess dosing and diary compliance, concomitant medications, and AE's.

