  - Subjects must have had a contrast enhanced computed tomography (CT) or magnetic resonance imaging (MRI) scan of the brain within 60 months of the Screening Visit and an EEG within 24 months of the screening visit. However, if clinical symptoms have emerged or a change in a clinical status has occurred such that an imaging study would be required, then a CT with contrast or MRI of the head should be performed regardless of the amount of time that has elapsed since the previous CT/MRI scan. Results must be available as soon as possible following screening and must be completed and reviewed prior to enrollment. Imaging results must be consistent with the diagnosis of focal-onset epilepsy and must demonstrate that no abnormality is likely to be progressive.
  - Subjects must have had an average of at least 3 seizures per month in the 3 months prior to screening.
5. Currently receiving a stable regimen of 1 to 3 antiepileptic treatments (stable within 28 days prior to screening). Benzodiazepine medication used on a regular basis at a stable dosage will be considered 1 of the concurrent antiepileptic treatments. Any PRN benzodiazepine use in addition to AEDs must be discussed with the Pfizer clinician and allowance will be decided on a case-by-case basis. The vagus nerve stimulator (VNS) is allowed and considered 1 of the 3 antiepileptic treatments.
6. A 12-lead ECG at screening without clinically significant abnormal findings as determined by the investigator.

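### For direct enrollers who need a new CT/MRI, Protocol Section 6.2 allows the scan to be read after the first dose, against inclusion criterion 4 and the screening-before-dose rule

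*Protocol*

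**What the plan says.** Protocol Section 6.2 covers Visit 1B, the screening visit for children who enter without having been in a parent study. It lists a contrast CT or MRI among the screening procedures, to be done if there is no scan within 60 months or if one is clinically warranted. A note then relaxes the timing: "it should be performed as soon as possible after Visit 1 if it cannot be performed on the day of this visit". The deadline in that note is that the scan "must be completed and reviewed prior to Visit 2".

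Further down the same Visit 1B list is the instruction "Administer first dose of study medication in office". The note directly under it reads "all screening procedures must be completed before subject is administered the first dose of study medication". It goes on to let eligibility be confirmed by Visit 2 and gives a route for a child who fails: "If a subject is not deemed eligible, subject should be notified by phone to discontinue study medication", followed by an early termination visit.

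Two other places set the order:

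- **Section 4.1.1, inclusion criterion 4**, on imaging: "Results must be available as soon as possible following screening and must be completed and reviewed prior to enrollment". The criterion also requires the scan to fit focal-onset epilepsy and to show nothing likely to progress.
- **Schedule of Activities, footnote j**: "All screening procedures must be completed prior to administration of first study medication".

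The openings of Sections 4.1.1 and 4.2, and the second sentence of footnote j, allow direct enrollers' eligibility to be confirmed up to and including Visit 2. Visit 2 falls on Day 8 ±1 (Section 6.3).

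**The concern.** A site that uses the imaging note and works down the Visit 1B list can give study drug to a child whose scan has not been taken. Doing so breaks the rule printed a few lines later in the same section, and it breaks the inclusion criterion that the scan is there to satisfy.

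The scan decides eligibility. Criterion 4 needs it to rule out a progressive abnormality, and exclusion criterion 4 in Section 4.2 bars a progressive structural CNS lesion. The children affected are those with no recent scan and those with new symptoms or a change in clinical status. In the second group a new lesion is a particular worry.

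Two things are at stake. A child who should have been excluded may be exposed to study drug, and the protocol's own text would then generate deviations. Under SAP Section 5.1 one dose puts such a child in the Safety population, so the child would also appear in the summaries and not only in the deviation listing.

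**Working it through.** The plan states no figure on this point. The check compares the timing rules and then sizes the window.

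**Step 1: the rules side by side**

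| Place in the Protocol | What it fixes | Latest time allowed |
|---|---|---|
| 6.2, imaging note | Scan done and reviewed | Before Visit 2 |
| 6.2, visit list | First dose | At Visit 1B |
| 6.2, note under first dose | All screening procedures done | Before first dose |
| Schedule, footnote j | All screening procedures done | Before first dose |
| 4.1.1, criterion 4 | Imaging done and reviewed | Before enrolment |
| 4.1.1 and 4.2 openings, 6.2, footnote j | Eligibility confirmed | On or before Visit 2 |

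**Step 2: can they all be met?** Suppose the scan is deferred under the first row and the dose is given under the second. The third row then fails, because Section 6.2 itself lists the scan as a screening procedure. The fifth row also fails, on the assumption that a child who has taken study drug is enrolled. The third-row conflict does not need that assumption.

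**Step 3: does the Visit 2 allowance rescue it?** Footnote j and the Section 6.2 note each state two separate rules: procedures are finished before the first dose, and eligibility is confirmed by Visit 2. Together they mean that the test is performed first and its result may come later. This fits laboratory tests, where the sample is taken at Visit 1B and Section 6.2 gives a specific stop route for an abnormal value. It does not cover a scan that has not been performed, and it does not alter the review requirement in criterion 4.

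**Step 4: size of the window**

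- First dose: Day 1.
- Visit 2: Day 8 ±1, so Day 7 to Day 9.
- Latest review, the day before Visit 2: Day 6 to Day 8.
- Time from first dose to review: 6 − 1 = 5 days to 8 − 1 = 7 days.

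Over 5 to 7 days at the starting dose:

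- Twice daily: 5 × 2 = 10 to 7 × 2 = 14 doses. Three times daily: 5 × 3 = 15 to 7 × 3 = 21 doses.
- At 30 kg or more: 2.5 mg/kg/day × 5 to 7 = 12.5 to 17.5 mg/kg, capped at 150 mg/day × 5 to 7 = 750 to 1,050 mg.
- Under 30 kg: 3.5 mg/kg/day × 5 to 7 = 17.5 to 24.5 mg/kg.

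These totals describe exposure. They do not measure risk.

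**The case against.** The best defence is that the Visit 2 allowance is deliberate. It appears in four places, and the Document History says Amendment 2 clarified eligibility assessment for direct enrollers. Section 6.2 accepts dosing before laboratory results are back, even creatinine for a renally cleared drug, and provides a telephone stop. Criterion 4 itself speaks of results soon after screening. On this view imaging is simply one more result that may arrive within the first week. The point about results stands. It does not extend to a procedure not yet performed, and the same sentence of criterion 4 still requires review before enrolment.

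A second defence is that a careful site would reconcile the texts by holding the dose until the scan is read. That reading is available and is probably the safer one. But the protocol does not say so, and it describes no dosing visit between Visit 1B and Visit 2.

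A reader might also infer more than the documents support:

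- **Footnote a** of the Schedule says direct enrollers "must complete all of the screening assessment noted under Visit 1B". It gives no order relative to the dose, so it is not a further contradiction.
- **Footnote j** is indirect support only. The Schedule as available here shows no imaging row, so the clearest statement of the rule is the one in Section 6.2.
- **Section 5.1** starts treatment in those who complete Visit 1 and are eligible. It can be read together with the Visit 2 allowance and is not clearly contradicted.
- **Harm from the drug.** No text says that about a week at the starting dose endangers a child with a progressive lesion. Section 3.1 lets the starting dose be stopped without a taper.
- **Suicidality screening** is a separate matter. Sections 7.6.1 and 7.6.4 already hold entry until CBCL scores, and any required risk assessment, are in hand.

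**Conclusion.** The conflict is real and should be fixed. The Section 6.2 imaging note cannot be used together with dosing at Visit 1B without breaking both the screening-before-dose rule in that section and inclusion criterion 4.

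The consequence is bounded. A child with an excluded lesion could take the starting dose for about 5 to 7 days, or less if the scan is read sooner and the telephone stop is used. This assumes dosing on Day 1, Visit 2 within its window, and review no later than the day before. It can arise only for direct enrollers with no CT/MRI within 60 months or with a clinical reason for a new one, and only when the scan cannot be done and read on the day. The documents do not say how many that is, and it could be none.

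The documents support a finding of avoidable exposure of a possibly ineligible child and a deviation built into the text. They do not support a finding of demonstrated harm from pregabalin.

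**What to change.** In the Section 6.2 imaging note, replace the Visit 2 deadline with: *prior to the first dose of study medication; if the scan cannot be done and read on the day of Visit 1B, drug and diary dispensing and the first dose are withheld until it is reviewed.*

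Consequential edits:

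- In Section 4.1.1 and in the Section 6.2 note on eligibility, state that required imaging is an exception to confirmation by Visit 2.
- In Section 3.1, which starts the seizure diary at Visit 1, start it at the first dose for these children. Otherwise days before treatment would enter the Week 1 rate, because SAP Section 6.2.3 counts from the first diary entry.
- Treat the day of first dose as Day 1 for these children, and count Visit 2 from it.
- Set a short maximum interval from screening to first dose, after which the pregnancy test, laboratory tests and suicidality assessment are repeated. The documents give no figure, so the sponsor must choose one.

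The SAP need not change. Baseline for direct enrollers is Visit 1B (Section 8), exposure already runs from the date of first dose (Section 8.3.11), and any repeated tests would serve eligibility only.

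The cost is a protocol amendment, IVRS handling that assigns a number at screening without dispensing, and a short delay with one return visit for affected children. Others are untouched.
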